#### Rationale:

A first study, VYF01, aimed to assess the safety, viremia and immune responses of 3 dosages of vYF and YF-VAX, as a control vaccine, is ongoing in the USA. A second planned study, VYF02, aims to assess the non-inferiority of the immune response of the investigational vaccine candidate vYF to the licensed YF-VAX vaccine in adults in the USA.

The proposed third study VYF03 is a Phase II, randomized, observer-blind, active-controlled (Stamaril) multi-center study to assess the non-inferiority of the immune response, in terms of seroconversion rates of the investigational vaccine candidate vYF to the licensed Stamaril, in adults aged 18 years up to 60 years in Europe (EU). The safety and immunogenicity profile of vYF in a cohort of Asian population of Chinese origin outside of China will also be presented. The study will also assess the immunogenicity profiles (seroprotection rates, geometric mean of titers [GMT] and geometric means of the individual titer ratios [GMTR]) and the safety profiles of vYF and Stamaril.

Stamaril, the Sanofi Pasteur YF vaccine currently licensed and in use in more than 100 countries (including European and some Asian countries) will be the control vaccine.

For the non-inferiority VYF03 study in EU, it is planned to enroll 570 participants into 2 groups in a 2:1 ratio: 380 participants will be administered vYF and 190 participants will be administered Stamaril on D01. In VYF03 in Asia, it is planned to enroll 120 participants also distributed into 2 groups in a 2:1 ratio: 80 participants will be administered vYF and 40 participants will be administered Stamaril on D01. The participants in Asia (80 and 40 in the vYF and Stamaril groups, respectively) will be enrolled for descriptive purposes only.

In addition, the study aims to assess the immune responses induced by the YF vaccines in terms of seroprotection and seroconversion rates, GMT, GMTR, depending on FV serostatus at baseline (eg, YF, Dengue and Zika viruses, as well as Japanese encephalitis [JE] virus in Asia), as well as the safety profiles. The persistence of the immune response over time, up to 5 years post-vaccination, will be assessed yearly.

VYF03 assessment will be based on immunogenicity and safety profiles of the vYF vaccine in comparison to Stamaril.

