The YF neutralizing antibody titers will be determined in a microneutralization (MN) assay that was developed by Sanofi Pasteur and currently in use in VYF01. An interim analysis on the first 37 randomized participants (36 of them vaccinated with either vYF 4 Log CCID50/dose, 5 Log CCID50/dose, 6 Log CCID50/dose, or YF-VAX) shows that GMTs well above the threshold of protection (10, 1/dil) were observed in all vaccine groups on D28 post vaccine administration (Per-Protocol analysis in YF-naïve populationa) and that 100% of YF-naïve participants seroconvertedb and were seroprotected on D28. The satisfactory safety profile of all vYF dosage groups and the measurement of quantified viremia over time from D01 to D15 completed the interim analysis. Therefore, the dosage of 5 Log CCID50/dose is deemed appropriate for the next phases of the clinical development of vYF, starting with VYF02, which is the first non-inferiority study in adults.

VYF03 is designed to assess the immune response and the maintenance of the antibody titers over time, up to 5-years post vaccine administration as the existing YF vaccines are well known for inducing a long-lasting immunity. In addition, a subset of participants will be assessed on D11 to describe the early immune response induced in the 2 vaccine groups.

a YF-naïve population, or YF negative population, corresponds to participants with no pre-existing (ie, no detectable as below LLOQ equal to 10 (1/dil) which also defines the threshold for protection) Ab titers. Those participants are given a value equal to half LLOQ, ie, 5 (1/dil).

\_

<sup>b In VYF01, seroconversion is achieved for a 4-fold increase as compared to pre-vaccination value; and in YF-naïve participants seroconversion is achieved for a value equal or greater than 40 (1/dil).

The AESIs that are considered for the development of vYF were defined based on the knowledge of those associated to existing YF vaccines licensed by Sanofi Pasteur (YF-VAX and Stamaril):

- Serious hypersensitivity/allergic reactions
- Organ failure/serious viscerotropic events
- Serious neurologic events

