# 8.1.2.1 Immunogenicity Endpoints

For all objectives, YF antibody assessments will be performed using the YF MN assay.

For the primary objective, seroconversion will be assessed 28 days post-vYF (administered on D01) and post-Stamaril (administered on D01) in YF-naïve participants.

For the secondary objectives, YF antibody assessments will be performed as follows for each group:

NAb titers at D01, D11 (subset only), D29, M6, and yearly from Y1 to Y5

Derived endpoints are:

• Seroconversion rates at D11 (subset only) and D29, M6, and yearly from Y1 to Y5

Seroconversion is defined as a 4-fold increase in NAb titers: i) as compared to the D01 titers at each time point up to M6; ii) as compared to the last planned previous time point from Y1 onwards

- Seroprotection rates based on participants with antibody titers  $\geq 10$  (1/dil) at baseline (D01) and at D11 (subset only), D29, M6, and yearly from Y1 to Y5
- GMTRs for D11/D01 (subset only), D29/D01, M6/D01 and yearly ratios.

The corresponding parameters are seroconversion rate, seroprotection rate, GMT, and GMTR

Data will be analyzed depending on FV immune status at baseline (FV-naïve and immune: YF-naïve and immune, Dengue serotypes 1-4 naïve and immune, Zika-naïve and immune, and JE-naïve and immune in participants enrolled in Asia)

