## 2.2 Secondary Objective(s)

#### Immunogenicity

If the primary objective is reached on D29 with revised time window of +6 days (instead of +3 days, as initially planned in the protocol), the secondary objective is to demonstrate the non-inferiority of the antibody response in terms of seroconversion rates 28 days after vaccine administration of one dose of vYF (administered on D01) compared to the antibody response after one dose of the Stamaril control vaccine (administered on D01) in participants enrolled in EU in YF-naïve participants, with a time window of +3 days.

To describe the antibody immune responses to YF in both vaccine groups in EU and in Asia before (D01) and after (D11 in a subset of participants only, and D29, M6, and yearly from Y1 to Y5 in all participants) vYF or Stamaril administration.

To describe the immune response to YF in both vaccine group using YF MN assays between D01 and D29 using the D29 +3 days time window in EU YF-naïve participants.

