both vaccine groups before (D01) and after vYF or Stamaril administration, on D11 (in a subset† of participants only), D29, M6, and yearly from Y1 to Y5 in all participants	
 
follows for each group:
 
NAb titers at D01, D11 (subset only†), D29, M6, and yearly from Y1 to Y5
 
Derived endpoints are:
 
Seroconversion rates at D11 (subset only†) and D29, M6, and yearly from Y1 to Y5
 
Seroconversion is defined as a 4-fold increase in NAb titers: i) as compared to the D01 titers at each time point up to M6; ii) as compared to the last planned previous time point from Y1 onwards
 
Seroprotection rates based on participants with antibody titers ≥ 10 (1/dil) at baseline (D01) and at D11 (subset only†), D29, M6, and yearly from Y1 to Y5
 
Geometric means of the individual titer ratios (GMTRs) for D11/D01 (subset only†), D29/D01, M6/D01 and yearly ratios.
 
	
	The corresponding parameters are seroconversion rate, seroprotection rate, GMT, and GMTR. Data will be analyzed depending on FV immune status at baseline (FV- naïve and immune: YF-naïve and immune, Dengue serotypes 1-4 naïve and immune, Zika-naïve and immune, and JE-naïve and immune in participants enrolled in Asia)	
• To describe the immune response to YF in both vaccine groups using YF MN assays between D01 and D29 using the D29 +3 days time window in EU YF-naive participants.	
 
Seroconversion rates at D29
 
Seroprotection rates at baseline (D01) and at D29
 
Geometric means of the individual titers ratios for D29/D01
 
	

Objectives	Endpoints	Assessment	

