## 5.1.2.2 Statistical Methods

#### Immunogenicity:

Analyses will be performed on the Full Analyses Set.

The immunogenicity parameters will be described per vaccine group. Immunogenicity analyses will be provided on participants by YF serostatus and by FV serostatus.

The following parameters will be analyzed:

- GMT for each vaccine group
- Seroconversion rates: number and percentage of participants in each vaccine group converted with neutralizing antibody titer 4-fold increased compared to D01 up to M6: D11 (subset only) compared to D01, D29 compared to D01, M6 compared to D01; and yearly from Y1 to Y5 compared with the latest planned timepoint: Y1 compared to M6, Y2 compared to Y1, Y3 compared to Y2, Y4 compared to Y3, Y5 compared to Y4
- Within-group GMTR for each vaccine group post-vaccination injection, compared to D01 (D11/D01 [subset only], D29/D01, M6/D01 and yearly ratios: Y1/M6, Y2/Y1, Y3/Y2, Y4/Y3, Y5/Y4

- Number and percentage of participants (seroprotection rates) in each vaccine group with antibody titer ≥ 10 (1/dil) at baseline (D01) and at D11 (subset only†), D29, M6, and yearly from Y1 to Y5
- Distribution of titers against YF at each time point and corresponding RCDC

The 95% CIs will be calculated using:

- The normal approximate method for GMTs and GMTRs
- The exact binomial distribution for percentages (Clopper-Pearson's method, quoted by Newcombe)

Assuming that log10 transformation of the titers/ratios follows a normal distribution, first, the mean and 95% CI will be calculated on log10 (titers/ratios) using the usual calculation for normal distribution, then antilog transformations will be applied to the results of calculations, to compute GMTs/GMTRs and their 95% CIs.

Complementary immunogenicity analysis based on the planned analysis on D29 with a time window of +3 days will be performed on a sub-population of the Per-Protocol Analysis Set:

- Non-inferiority analysis of the antibody response on D29
- GMT for each vaccine group
- Seroconversion rates: number and percentage of participants in each vaccine group converted with neutralizing antibody titer 4-fold increase compared to the previous time point, at D29 compared to D01
- Within-group GMTR for each vaccine group D29 post-vaccination injection, compared to D01
- Number and percentage of participants (seroprotection rates) in each vaccine group with antibody titer  $\geq 10$  (1/dil) at baseline (D01) and at D29

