Flavivirus status: Immune for participants with quantified ( $\geq$  LLOQ) neutralizing Abs against YF, and/or against at least one dengue serotype, and/or Zika  $\geq$  100 (1/dil) in the baseline sample, and/or JE in Asia; naive for participants without quantified ( $\leq$  LLOQ) neutralizing Abs against YF, with no Ab quantified against any of the four dengue serotypes, Zika  $\leq$  100 (1/dil) and JE in Asia; in the baseline sample.

 Table 7.4: Summary of percentages of participants achieving seroconversion after one dose YF vaccination by YF status at baseline 

 Microneutralization assays - Full Analysis Set

YF status	Time point		vYF (N=xxx)			Stamaril (N=xxx)			
		Seroconversion rate			S	Seroconversion rat	te		
		n/M	(%)	95% CI	n/M	(%)	95% CI		
Immune	V02 (V01+10D)/ V01 (Pre-inj)	###/###	##.#	(##.#; ##.#)	###/###	##.#	(##.#; ##.#)		
	V04 (V01+28D)/ V01 (Pre-inj)	###/###	##.#	(##.#; ##.#)	###/###	##.#	(##.#; ##.#)		
	V05 (V01+6M)/ V01 (Pre-inj)	###/###	##.#	(##.#; ##.#)	###/###	##.#	(##.#; ##.#)		
	V06 (V01+1Y)/ V05 (V01+6M)	###/###	##.#	(##.#; ##.#)	###/###	##.#	(##.#; ##.#)		
	V07 (V01+2Y)/ V06 (V01+1Y)	###/###	##.#	(##.#; ##.#)	###/###	##.#	(##.#; ##.#)		
	V08 (V01+3Y)/ V07 (V01+2Y)	###/###	##.#	(##.#; ##.#)	###/###	##.#	(##.#; ##.#)		
	V09 (V01+4Y)/ V08 (V01+3Y)	###/###	##.#	(##.#; ##.#)	###/###	##.#	(##.#; ##.#)		
	V10 (V01+5Y)/ V09 (V01+4Y)	###/###	##.#	(##.#; ##.#)	###/###	##.#	(##.#; ##.#)		
Naive	•••						· · · · ·		

n: Number of participant s who achieve a yellow fever vaccination seroconversion.

M: Number of participant s with available data for the endpoint.

Seroconversion: For a participant with a 4-fold increase in NAb titers as compared to the previous timepoint value

YF status: Immune for participants with quantified ( $\geq$  LLOQ) neutralizing Abs against YF; naive for participants without quantified (< LLOQ) neutralizing Abs against YF in the baseline sample.

 Table 7.5: Summary of percentages of participants achieving seroconversion after one dose YF vaccination by FV status at baseline 

 Microneutralization assays - Full Analysis Set

FV status	Time point		vYF (N=xxx)			Stamaril (N=xxx)			
		Seroconversion rate			S	Seroconversion ra	te		
		n/M	(%)	95% CI	n/M	(%)	95% CI		
Immune	V02 (V01+10D)/ V01 (Pre-inj)	###/###	##.#	(##.#; ##.#)	###/###	##.#	(##.#; ##.#)		
	V04 (V01+28D)/ V01 (Pre-inj)	###/###	##.#	(##.#; ##.#)	###/###	##.#	(##.#; ##.#)		

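### The Y1-Y5 seroconversion rows are referenced to the previous visit, so they stay low whether titres are maintained or wane and do not inform persistence

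*SAP*

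**What the plan says.** The definition is the same throughout. Protocol Table 3.1 and section 8.1.2.1 define seroconversion as a 4-fold rise over D01 up to M6, and after that "ii) as compared to the last planned previous time point from Y1 onwards". Protocol 9.4.2 lists the comparisons visit by visit. SAP 4.1 repeats the rule ("as compared to the last planned previous time point from Y1 onwards"), and SAP 5.1.2.2 spells it out: "yearly from Y1 to Y5 compared with the latest planned timepoint: Y1 compared to M6, Y2 compared to Y1", continuing to Y5 against Y4. The GMTRs use the same pairs. After M6, neither seroconversion nor GMTR is referenced to D01 or D29.

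The yearly rows appear in SAP Table 7.4, titled "Summary of percentages of participants achieving seroconversion after one dose YF vaccination by YF status at baseline", and in Table 7.5 by FV status, in the same columns as the D29 and M6 rows. The footnote reads "Seroconversion: For a participant with a 4-fold increase in NAb titers as compared to the previous timepoint value". That footnote does not fit the M6 row, which is labelled as V05 against V01.

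The long follow-up has a stated purpose. The protocol synopsis says: "The persistence of the immune response over time, up to 5 years post-vaccination, will be assessed yearly". Protocol 2.1 says the study is designed to assess the immune response and "the maintenance of the antibody titers over time, up to 5-years post vaccine administration". The formal secondary objective is broader and descriptive: "To describe the antibody immune responses to YF in both vaccine groups in EU and in Asia before (D01) and after" vaccination, at visits out to Y5. SAP 5.1.2.1 states that no secondary hypotheses are tested.

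**The concern.** A row called seroconversion after one dose should tell the reader how many participants still hold the response to that dose. From Y1 the planned row answers a different question: how many rose 4-fold since the last visit. A participant who holds a protective titre for five years counts as not seroconverted at every yearly visit, and so does one whose titre steadily disappears.

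In the VYF01 interim data cited in Protocol 2.1, all YF-naïve participants had seroconverted at D28. If D29 looks similar here, the column will show a high rate followed by very low ones, which a hurried reader could take for loss of response.

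The few positives at Y1-Y5 will come from noise, natural exposure or a further YF vaccination. Under Protocol 2.3.2, sites receive listings of group assignment after the first interim analysis. vYF recipients are told they need a licensed vaccine before travel to endemic areas, while Stamaril recipients can receive the vaccination certificate. Non-study YF vaccination could therefore differ by arm. Protocol 6.5 records it for the whole study, but the SAP has no rule for titres taken afterwards: the FAS definition in SAP 5.2 does not exclude them.

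**Working it through.** **1. The plan's own figure.** SAP 4.1 sets the threshold for a baseline-seronegative participant at 20 (1/dil). With LLOQ 10 and half-LLOQ 5, 4 × 5 = 20. For a baseline of 10, 4 × 10 = 40, as in Protocol 8.1.2.2. Both reproduce. The yearly rows have no stated power or alpha to check.

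**2. Logic.** A 4-fold rise needs a log10 difference of at least log10 4 = 0.602. A stable titre has a true difference of 0. A titre halving each year has −0.301. Neither reaches the threshold without measurement error or a real boost.

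**3. Noise-only rate.** Let s be the SD of one log10 titre and d the true yearly decline in log10. Then P(4-fold rise) = 1 − Φ((0.602 + d)/(s√2)). Protocol 8.1.2.2 says precision was assessed but gives no figure, so s is an assumption, shown over a range.

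| s (log10, assumed) | s√2 | Stable titre (d = 0) | Halving yearly (d = 0.301) |
|---|---|---|---|
| 0.15 | 0.212 | z = 2.84, 0.2% | z = 4.26, 0.0% |
| 0.20 | 0.283 | z = 2.13, 1.7% | z = 3.19, 0.1% |
| 0.30 | 0.424 | z = 1.42, 7.8% | z = 2.13, 1.7% |

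**4. Do the rows separate good from poor persistence?** This was simulated in 400,000 participants. Assumptions: naïve at D01, GMT 640 at M6, between-person SD 1.5 log2, assay SD 0.5 log2 (0.15 log10), titres below 10 set to 5. Results at Y5:

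| Scenario | Planned row (Y5 vs Y4) | ≥ 4 × D01 | ≥ 10 (1/dil) | GMT |
|---|---|---|---|---|
| Full persistence | 0.2% | 99.9% | 100% | 638 |
| Halving yearly | 0.0% | 50.1% | 73.7% | 20 |
| Loss of 1.5 log2 per year | 0.0% | 5.6% | 17.1% | 6.2 |

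The planned row does not separate the three cases. The other three measures do.

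**5. Non-study vaccination.** Suppose 2% of participants per year were revaccinated and boosted to at least 4 times the M6 GMT (both assumed). The planned row is then about 1.2% under full persistence and 1.0% to 1.8% under yearly halving, so revaccination drives it more than persistence does. In the halving case the other Y5 measures also move: GMT from 20 to 32, the ≥ 10 rate from 73.7% to 76.2%, and the ≥ 4 × D01 rate from 50.1% to 54.9%. A D01 reference alone does not remove this.

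**6. Can the yearly GMTRs be chained to give overall decay?** Not reliably. SAP 4.2.1.1 sets a value below LLOQ to 5 in a numerator and 10 in a denominator. The sequence 20, < 10, 20 gives 5/20 = 0.25, then 20/10 = 2, with product 0.5, although the overall ratio is 20/20 = 1. With no imputation (SAP 5.3.1), one missed intermediate yearly visit also removes two consecutive comparisons.

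**The case against.** The strongest reply is that persistence is already covered. SAP 5.1.2.2 plans GMTs, seroprotection (≥ 10) at every yearly visit, and titre distributions with reverse cumulative curves at each time point. Tables 7.2, 7.3, 7.6 and 7.7 and Figures 7.1-7.4 carry these to Y5. This stands. A reader might infer from the seroconversion definition that the trial cannot answer its persistence aim; the documents do not support that, because only these rows fail.

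The definition is also prespecified, the same in both documents, and visible in row labels that name both visits. The rows are descriptive, and the formal secondary objective does not mention persistence. All of this is true and limits the consequence, but it does not make the rows informative.

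In YF-naïve participants a 4-fold rise over D01 is a titre of at least 20, which can be read from the naïve-stratum curve. This stands in part: a curve gives no tabulated rate with a confidence interval, and the equivalence does not hold in the YF-immune stratum, where D01 values vary.

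A reader might also infer that later seroconversions will cluster in the vYF arm. The documents show only that this could happen. The advice applies before endemic travel, no uptake is given, and a revaccinated person with a maintained titre need not rise 4-fold.

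**Conclusion.** The point holds for the yearly seroconversion rows of Tables 7.4 and 7.5. They will be low under full persistence and under steady loss alike, so they do not inform the stated aim of assessing maintenance of titres to 5 years. The GMTR switch is a lesser matter: year-on-year ratios do show decay step by step, but no ratio spans the whole follow-up.

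Noise alone gives about 0.2% to 7.8% per year for stable titres at assay SDs of 0.15 to 0.30 log10, and about 0.0% to 1.7% if titres halve yearly. It would be wrong to read the upper figure as applying whatever the persistence: it needs unchanged titres and the largest assumed SD. The logic in step 2 needs no assumption; the percentages rest on the assumed SDs and simulation inputs.

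The primary non-inferiority conclusion is untouched. The change is worth making because it is cheap and turns planned rows into informative ones.

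**What to change.** - In SAP 4.1 and 5.1.2.2 and Tables 7.4 and 7.5, reference Y1-Y5 seroconversion to D01, as is already done up to M6.
- In SAP 4.1 and 5.1.2.2 and Tables 7.2 and 7.3, add the GMTR of each yearly visit to D29 or D01.
- Keep the year-on-year 4-fold rise only as a separately named flag for possible exposure or revaccination. State how a previous titre below LLOQ enters it: the SAP gives no rule, and the cut-off is 20 if 5 is used or 40 if 10 is used.
- Present Y1-Y5 results also without titres taken after a recorded non-study YF vaccination, with the number removed per arm.
- Correct the footnote of Tables 7.4 and 7.5 so that it matches the row labels.
- Record the change in SAP 5.7 as a departure from Protocol Table 3.1 and sections 8.1.2.1 and 9.4.2.

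The cost is a documented departure from the protocol definition and some extra table work. No new data are needed, since the titres and non-study YF vaccinations are already collected.

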#### Safety:

Safety results will be described per vaccine groups on the SafAS. The main parameters for the safety endpoints will be described by 95% CIs of point estimates, calculated using the exact binomial distribution from Clopper-Pearson's method quoted by Newcombe (2) for proportions.

#### 5.1.3 Statistical Methods for Exploratory Objective(s)

Analyses will be performed on the Randomized Set.

• GMT of NAb levels against FV infection (dengue, Zika, and JEV) for each vaccine group at baseline

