# 9.4.3 Exploratory Endpoint(s)

Exploratory endpoints are NAb levels against FV infection (dengue, Zika, and JEV) in blood samples taken at baseline.

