## 2.3 Exploratory Objective(s)

To describe the serological status of FV infection (dengue and Zika in all participants in EU and Asia; Japanese encephalitis [JE] in Asia) in the study population at baseline

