
 
Safety
 
To describe the safety profile of the vYF vaccine in comparison to the safety profile of the control Stamaril
 
To describe the safety of vaccination in all participants up to 28 days after vaccination
 
To describe all serious adverse events (SAEs) up to 6-month follow-up
 
To describe related SAEs and all deaths from D01 to 5 years after vaccination
 
To describe all AESIs up to 6-month after vaccination‡
 
	
 
Presence, nature (Medical Dictionary for Regulatory Activities [MedDRA] preferred term), duration, intensity and relationship to vaccination of any unsolicited systemic adverse events (AEs) reported in the 30 minutes after vaccination
 
Presence, time to onset, number of days of presence, and intensity of solicited (pre-listed in the participant's diary and electronic case report form [eCRF]) injection site reactions up to 7 days after vaccination solicited
 
Presence, time to onset, number of days of presence, and intensity of solicited systemic reactions up to 14 days after vaccination
 
Presence, nature (MedDRA preferred term), time to onset, duration, intensity, and relationship to vaccination (for systemic AEs only) of unsolicited (spontaneously reported) AEs, up to 28 days after vaccination
 
Presence of any SAEs and AESIs, up to 6-month after vaccination
 
Presence of related SAEs and all deaths from D01 to 5 years after vaccination
 
	See Section 8.1.2 of the protocol.	
Exploratory			
To describe the serological status of FV infection (dengue and Zika in all participants in EU and Asia; JE in Asia) in the study population at baseline	• NAb levels against FV infection (dengue and Zika in all participants in EU and Asia; JE in Asia) on a blood sample taken at baseline	See Section 8.1.2 of the protocol.	

AESI: adverse event of special interest; D: day; eCRF: electronic case report form; FV: flavivirus; GMT: geometric means of titer; GMTR: geometric means of titer ratios; M: month; MN; microneutralization; NAb: neutralizing antibody; Y: year

\* YF-naïve participants (or negative) at baseline correspond to participants with no detectable YF antibody (Ab) titers before vaccination. YF seronegative at baseline is defined as a titer < LLOQ for the assay (any participant with a

baseline titer  $\geq$  LLOQ will be eliminated from the primary analysis [Per-protocol analysis]).

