#### 4.2.1.4 Baseline Serostatus

The baseline serostatus (eg, YF naïve participants and YF immune, Dengue naïve and Dengue immune, Zika naïve and Zika immune in EU and Asia; JE-naïve and immune in Asia) is defined as the presence of antibodies (Abs) in the baseline blood sample collected at Visit 1 (V01) in the present study from all participants.

YF naïve participants are participants with baseline YF NAb value below the threshold for protection [< 10 (1/dil)]. If the NAb value is  $\geq$  10 (1/dil) then the YF immune indicator will be "Immune". Otherwise, the baseline YF serostatus will be classified as "Undetermined".

Dengue serostatus at baseline will be determined using a Dengue Plaque Reduction Neutralization Test (PRNT) assay for dengue serotypes 1 to 4. The serostatus of dengue is computed based on values of dengue NAb titers against each of the four serotypes at V01. If the NAb value is positive ( $\geq 10 [1/dil]$ ) for any serotype, then the dengue immune indicator will be "Immune". Else if the NAb value is not positive (<10 [1/dil]) and non-missing for all four serotypes (ie, all of the titers planned to be measured at baseline must be available, and valid [not coded "NR" in the serology database] then the dengue immune indicator will be "Naive". Otherwise, the baseline serostatus will be classified as "Undetermined".

Zika serostatus will be determined using a Zika microneutralization test for serum samples obtained at baseline. Zika immune samples were defined as having a Zika antibody titer of  $\geq$  100 (1/dil) (1). If the NAb value is not positive (< 100 [1/dil]) and non-missing (ie, the titers planned to be measured at baseline must be available, and valid [not coded "NR" in the serology database]), then the Zika immune indicator will be "Naive". Otherwise, the baseline Zika serostatus will be classified as "Undetermined".

JE serostatus will be determined using a JE PRNT assay for serum samples obtained at baseline. JE immune samples are defined as having a JE antibody titer of  $\geq 10$  (1/dil). If the NAb value is not positive (< 10 [1/dil]) and non-missing (ie, the titers planned to be measured at baseline must be available, and valid [not coded "NR" in the serology database]), then the JE immune indicator will be "Naive". Otherwise the baseline JE serostatus will be classified as "Undetermined".

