Flavivirus immune participants at baseline are defined as participants either immune to YF or immune to Dengue or immune to Zika at baseline (as well as JE in Asia). Flavivirus naive participants at baseline are defined as participants naïve to YF and naive to Dengue and naive to Zika at baseline (as well as JE in Asia). Otherwise the baseline Flavivirus serostatus will be classified as "Undetermined".

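### SAP 5.1.3 summarises baseline flavivirus serological status by a GMT per vaccine group pooled over EU and Asia; it should lead with the percentage immune by virus and region

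*SAP*

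**What the plan says.** SAP 2.3 states the exploratory objective as "To describe the serological status of FV infection" at baseline, covering dengue and Zika in both regions and JE in Asia. The matching endpoint in SAP 4.1 is "NAb levels against FV infection (dengue and Zika in all participants in EU and Asia; JE in Asia) on a blood sample taken at baseline". Protocol 9.4.3 repeats the endpoint ("Exploratory endpoints are NAb levels against FV infection (dengue, Zika, and JEV) in blood samples taken at baseline") and gives no method.

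The method is in SAP 5.1.3: "Analyses will be performed on the Randomized Set", followed by a single item, "GMT of NAb levels against FV infection (dengue, Zika, and JEV) for each vaccine group at baseline". It mentions neither a number or percentage immune nor region.

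SAP 4.2.1.4 derives a status of Immune, Naive or Undetermined for each virus. Dengue is immune if any serotype reaches 10 (1/dil), and JE uses a cutoff of 10. For Zika the cutoff is higher: "Zika immune samples were defined as having a Zika antibody titer of" at least 100. A composite is also derived: "Flavivirus immune participants at baseline are defined as participants either immune to YF or immune to Dengue or immune to Zika at baseline", with JE added in Asia.

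SAP 4.2.1.1 sets titres below the LLOQ to LLOQ/2 when GMTs are computed.

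**The concern.** The objective asks about status, and the named summary is a mean level. At baseline, a reader wants to know what fraction of participants had prior dengue, Zika or JE immunity, and how that differs between the European and Asian cohorts. Protocol 4.2 expects few flavivirus-experienced participants in EU, so region is where a difference would be looked for. Vaccine group is randomised, so at baseline it serves mainly as a balance check.

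At stake is whether the planned output answers the exploratory question. The same counts also help in reading the YF response by composite flavivirus status (SAP Tables 7.3, 7.5 and 7.7). JE enters that composite only in Asia, so the immune stratum is not defined identically in the two regions.

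**Working it through.** The plan states no figure for this objective, so there is nothing to reproduce. The question is whether a GMT identifies the share immune. Prevalences and titres below are assumptions for illustration; the documents give none.

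**Inputs from the documents**
- Value for a titre below the LLOQ in a GMT: LLOQ/2 = 10/2 = 5 (SAP 4.2.1.1; LLOQ of 10 for the dengue, Zika and JE assays in Protocol 8.1.2.2).
- Zika immune cutoff: 100 (SAP 4.2.1.4).
- Planned sizes (SAP 5.5): vYF 380 EU + 80 Asia = 460; Stamaril 190 + 40 = 230; total 570 + 120 = 690. Asia is 120/690 = 17.4%, and the same share in each arm.

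**Formula.** If a share p is positive with geometric mean g and the rest are set to 5, then GMT = 5 × (g/5)^p. One number depends on two unknowns, p and g.

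**Step 1: same GMT, different prevalence**
- p = 5%, g = 80: 5 × 16^0.05 = 5.74.
- p = 20%, g = 10: 5 × 2^0.20 = 5.74.

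Prevalence differs four-fold and the GMT is the same. Likewise a GMT of 10 fits 20% positive (g = 160), 50% (g = 20) or 80% (g = 11.9).

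**Step 2: Zika.** Titres of 10 to 99 are quantified, so they raise the GMT, but they are classed as naive. A Zika GMT of 40 arises if everyone has titre 40 (0% immune). It also arises if half have 320 and half are set to 5: √(320 × 5) = 40 (50% immune).

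**Step 3: pooling regions.** Assume 5% positive in EU, 80% in Asia and g = 100.
- EU: 5 × 20^0.05 = 5.8.
- Asia: 5 × 20^0.80 = 54.9.
- Pooled share: (570 × 0.05 + 120 × 0.80)/690 = 124.5/690 = 18.0%.
- Pooled GMT: 5 × 20^0.180 = 8.6, below the LLOQ of 10.

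Over four assumed pairs of prevalences (EU 2 to 10%, Asia 50 to 90%) with g = 100 or 200, the pooled GMT runs from 6.8 to 12.1, against 22 to 138 in Asia alone. This step concerns dengue and Zika. JE is tested only in Asian participants, so its GMT is already Asian.

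**Step 4: what the proposed summary would deliver.** Clopper-Pearson 95% CIs at the planned sizes, arms combined, for assumed prevalences of about 5% in EU and 50% in Asia:
- EU: 28/570, CI 3.3 to 7.0%.
- Asia: 60/120, CI 40.7 to 59.3%.

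**Step 5: other planned outputs.** SAP Tables 7.2 to 7.7 and Figures 7.1 to 7.4 report YF titres, seroconversion and seroprotection on the FAS, by YF status or composite flavivirus status. None of them splits by region or by individual virus.

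**The case against.** A reader might infer that the GMT is the only statistic that will ever be shown, that prevalence by virus will appear nowhere, or that a difference like that in step 1 would be invisible. The documents do not support those readings.

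- SAP Table 5.1 sets default descriptive statistics. For titres it lists log10 mean and SD, quartiles, minimum, maximum and a reverse cumulative distribution curve (RCDC). For categorical immunogenicity data, including cutoffs, it lists number and percentage with 95% CI. Applied to step 1, these would separate the two cases. The maximum is 80 against 10, the log10 SD is 1.204 × √(0.05 × 0.95) = 0.26 against 0.301 × √(0.20 × 0.80) = 0.12, and the curve at titre 10 reads 5% against 20%.
- A GMT is a natural summary of the endpoint as worded, antibody levels. For a level, including Zika titres of 10 to 99 is correct. The tension is with the objective's wording.
- SAP 4.1 commits to analysing the YF response by dengue, Zika and JE status. Such tables print the number in each stratum. The baseline rows of Tables 7.3 and 7.7 already do so for composite flavivirus status.
- SAP section 7 shows main outputs only and places the full shells in another document, so absence from the main shells does not prove that a table is unplanned.
- The mention of EU and Asia in the objective says who is tested for what; it does not promise a regional comparison. SAP 5.4 also allows an EU-only interim report if Asia is delayed.

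All of this stands as a limit on the point. What it does not do is assign a percentage immune, by virus and region, to this objective. Table 5.1 is generic, and SAP 5.1.3 does not invoke its cutoff row. An RCDC on the Randomized Set without a regional split would read 18% at titre 10 in step 3, which describes neither region. The stratum counts in the shown tables are on the FAS, for the composite, and not by region.

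**Conclusion.** The point holds in a limited form. SAP 5.1.3 names, for an objective about serological status, a level summary per vaccine group that pools the regions and does not determine the share immune. The endpoint wording supports keeping the GMT; it does not make it sufficient for the objective.

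The conclusion that a GMT cannot identify prevalence is arithmetic and needs no assumption beyond the LLOQ/2 rule. The sizes shown (5.74 in both cases; 8.6 pooled against 5.8 and 54.9) rest on assumed prevalences and titres, and the documents expect low flavivirus experience only for EU.

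Severity is low. The objective is exploratory and descriptive, and neither the primary analysis nor any hypothesis test is touched. This is a free improvement.

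**What to change.** In SAP 5.1.3:

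- Make the main summary the number, percentage and Clopper-Pearson 95% CI of Immune, Naive and Undetermined for dengue (any serotype) and Zika, by region (EU, Asia) and overall, and for JE in Asia.
- Add n and % at or above 10 (1/dil) for each dengue serotype, because SAP 4.2.1.4 derives one dengue status and not one per serotype.
- Keep the GMTs as a supplement, and give them by region as well.
- Keep the display by vaccine group as a balance check.

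Cost: one extra table. The statuses are already derived in SAP 4.2.1.4, the serotype counts are a threshold on titres already measured, and SAP section 5 already specifies the CI method. No new data, samples or tests are needed.
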